### **7.3.1 Sponsor Responsibility for Reporting Adverse Events**

Written IND safety reports will be submitted to the FDA by the IND sponsor, for serious, unexpected suspected adverse reactions within 15 calendar days of learning of its occurrence. If the event is fatal or is deemed to be life threatening, the report will be made within 7 calendar days. The IND sponsor will also make an assessment of whether the event constitutes an unanticipated problem posing risks to subjects or others (UP). This assessment will be provided to the Emory University IRB, which, in turn will make a final determination. If the Emory IRB determines an event is a UP it will notify the appropriate regulatory agencies and institutional officials.

## **8.0 STATISTICAL ANALYSIS PLAN**

### **8.1 Determination of Sample Size**

This is a 3+3 standard phase I trial design. The plan is to evaluate two dose cohorts- 45mg and 90 mg. An intermediate dose cohort (60 mg) will be evaluated only if we observe 2 or more DLT's in the 3 or 6 patients enrolled on the 90mg dose. If we observe 2 dose limiting toxicities on dose level 1, then the study will be completed with three patients (minimal number of patients). If we observe two DLT in the first three patients on dose level 1, the study will stop and the principal investigator will discuss at that point whether a lower dose level of XL888 should be tested. If we do not observe any dose limiting toxicities the study will require 9 patients. If we observe one dose limiting toxicity per dose level (maximum number of patient), then the study would require 18 patients. Therefore the phase part sample size can range from 3 to 18 patients. Expansion phase will be started once the recommended phase II dose (RP2D) is determined. Given minimal activity of checkpoint inhibitors in colorectal and pancreatic cancer, an overall response rate of the combination of PD-1 plus HSP90 inhibitor of 20% would be considered clinically significant. With an alpha of 0.1, and power of 80% (relaxed due to the pilot preliminary nature of this proposal) a total of 16 patients should be sufficient to make this determination. We will also obtain biologic endpoints with the paired biopsy samples that can help further develop the combination and understand its role in GI cancers. We plan to enroll 32 patients on the RP2D level with 16 patients per cohort (pancreas and colorectal cancer). Patients in the expansion phase will be assigned to treatment arms by PI (MK-3475 or MK-3475 plus XL-888). After the first 3 weeks all patients will receive the combination therapy. There is no planned comparison between the two arms. The aim of the expansion phase is to confirm the safety profile and tolerability of the regimen in patients with pancreatic and colorectal cancer.

The total number of patients will range from 38 to 50 patients.

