## 2.0 TRIAL DESIGN

Open label phase I trial. Primary objective is to determine the recommended phase 2 dose (RP2D) of the combination of XL888 and pembrolizumab. The design is 3+3 with 3 dose levels of XL888 (X). MTD is defined as the dose at which less than one-third of the subjects experience a DLT in the first 4 weeks of treatment.

After determining the RP2D, an additional 16 patients with pancreatic cancer (Arm A) and 16 patients with colorectal cancer (Arm B) will be enrolled in an expansion phase to confirm toxicity profile and obtain paired biopsies. Paired biopsy performed on 8 patients in each group. Patient selected for biopsy must have a primary or metastatic non-bone site that is amenable to safe biopsy. Bone only lesions are not suitable for biopsy. Patients undergoing paired biopsies will be assigned into two treatment cohorts (8 in each) and treated according to the schema below.

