**Dose level 3 will only be tested if we observe 2 DLT's on dose level 2.**

### 5.2.2 Dose Escalation

Starting dose of 45mg; if  $\geq 2$  patients with DLTs in 3 ( $\geq 2/3$ ) or 6 ( $\geq 2/6$ ) subjects; stop and consider reduced dose of XL888. If not, increase dose to 90 mg and test 3-6 patients. If  $\geq 2$  patients with DLTs in 3 or 6 subjects, reduce dose to 60 mg and try again. If an acceptable dose is identified, treat 16 more patients at the MTD. Prior to dose escalation, we will obtain approval from the Data Safety and Monitoring Committee (DSMC).

**5.2.3 Dose limiting toxicity (DLT)** will be defined as any of the following definitely treatment related adverse events during the first 21 days of therapy:

- Grade IV neutropenia lasting more than 8 days; any neutropenic fever or sepsis;
- Grade III with clinically significant bleeding or any grade IV thrombocytopenia;
- Grade III nausea, vomiting, or diarrhea, lasting  $>72$  hours despite adequate supportive care;
- Other non-hematologic treatment-related toxicity at Grade III or higher
- Grade 4 asymptomatic laboratory abnormalities that last for more than 24 hours or Grade 3 asymptomatic laboratory abnormalities lasting more than 21 days is a DLT.
- Grade IV or higher diarrhea, nausea, vomiting
- In ability to take more than 75% of XL888 due to toxicity.

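### Section 8.1 contradicts itself on how many patients must be treated at the dose carried forward: 9 patients with no DLTs implies six at 90 mg, the minimum total of 38 implies three, and no rule decides between them

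*Combined protocol and SAP*

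**What the plan says.** Section 8.1 describes the design in one line, "This is a 3+3 standard phase I trial design", and continues: "The plan is to evaluate two dose cohorts- 45mg and 90 mg". The intermediate 60 mg cohort "will be evaluated only if we observe 2 or more DLT's in the 3 or 6 patients enrolled on the 90mg dose". Section 5.2.2 rejects a dose on two or more DLTs in 3 or in 6 patients. After 45 mg it says: "If not, increase dose to 90 mg and test 3-6 patients". Section 2.0 adds that the "MTD is defined as the dose at which less than one-third of the subjects experience a DLT", with no minimum number of patients.

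On numbers, 8.1 gives 9 escalation patients if no DLT occurs, 18 as the escalation maximum, and 32 patients in the expansion. It then states: "The total number of patients will range from 38 to 50 patients". Section 2.0 describes the two groups of 16 as additional to the escalation patients. The expansion is tied to the RP2D alone: "Expansion phase will be started once the recommended phase II dose (RP2D) is determined".

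Section 8.2 has no stopping rule. Sections 5.2.2 and 10.5 require DSMC approval for dose escalation. Neither states it for opening the expansion.

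**The concern.** The RP2D is the primary objective, and the number of patients behind it is part of its decision rule. Two figures in the same section of the plan imply different numbers at 90 mg, and no sentence says which applies. For 60 mg no figure suggests six patients at all. A team following the text could declare the RP2D on 0 DLTs in 3 patients at that dose and open all 32 places. Another team reading the same text could treat six first. The two readings have different error rates, and after the choice no stated threshold or approval step corrects a wrong one.

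**Working it through.** **Inputs.** The cohorts, the 60 mg trigger, the rejection rule and the counts 9, 18, 32 and 38 to 50 come from 5.2.2 and 8.1. Two things are assumed. First, a cohort goes from 3 to 6 patients after 1 DLT in 3, which the plan does not spell out. Second, patients are independent with true DLT rate p; the documents give no rate for the combination, so a range is shown.

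**Step 1: the plan's total.** Each level takes 3 or 6 patients.
- RP2D at 90 mg: (3 or 6) + (3 or 6) = 6, 9 or 12.
- RP2D at 60 mg: three levels of 3 or 6 = 9, 12, 15 or 18.

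Escalation therefore takes 6 to 18 patients, and adding 32 gives 38 to 50, exactly the stated range. The lower end needs 38 − 32 = 6 = 3 + 3, that is, 90 mg accepted on 0/3.

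**Step 2: the figure of 9.** With no DLTs the same rules give 3 + 3 = 6, not 9. Since 60 mg does not open without DLTs, 9 fits only as 3 at 45 mg + 6 at 90 mg. Then 9 + 32 = 41. If six patients are required at the dose carried forward, and all 32 are additional, the total runs from 41 to 50.

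**Step 3: what the difference does.** Let q = 1 − p.
- Accept on 0/3 or 1/6: A = q³ + 3pq² × q³.
- Accept only on at most 1 in 6: B = q⁶ + 6pq⁵.
- A − B = P(0 of first 3) × P(2 or more of next 3).

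At p = 1/3: A = 0.2963 + 0.4444 × 0.2963 = 0.4280; B = 0.0878 + 0.2634 = 0.3512.

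| True DLT rate | Accepted on 0/3 | A | B | A − B (points) |
|---|---|---|---|---|
| 10% | 72.9% | 90.6% | 88.6% | 2.0 |
| 20% | 51.2% | 70.9% | 65.5% | 5.3 |
| 30% | 34.3% | 49.4% | 42.0% | 7.4 |
| 1/3 | 29.6% | 42.8% | 35.1% | 7.7 |
| 40% | 21.6% | 30.9% | 23.3% | 7.6 |
| 50% | 12.5% | 17.2% | 10.9% | 6.3 |

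Dividing the second column by the third, 69% to 80% of acceptances under A rest on three patients at that dose.

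**Step 4: whole-trial illustration.** Assume true rates of 10%, 20% and 40% at 45, 60 and 90 mg. The chance that the RP2D has a true rate above one-third is 0.9061 × 0.3093 = 28.0% under A and 0.9061 × 0.2333 = 21.1% under B. With 20%, 40% and 50%, both 60 and 90 mg count:
- A: 0.7086 × 0.1719 + 0.7086 × 0.8281 × 0.3093 = 30.3%.
- B: 0.7086 × 0.1094 + 0.7086 × 0.8906 × 0.2333 = 22.5%.

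**The case against.** The strongest reply is that the safeguard is already there: a design called standard, plus the figure of 9, points to six patients at 90 mg. This may be what was meant, but it is not secure. The 9 may instead be 3 patients at each of 3 levels, parallel to 18 = 6 × 3, even though the 60 mg trigger rules that out when there are no DLTs. The explanation given for 18 has the same flaw: one DLT per level would never open 60 mg and gives 6 + 6 = 12. Either way the 38 conflicts with the 9, and the reply does not reach 60 mg.

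A second reply is that six patients is a trade-off, not a clear gain. That stands. The rule is stricter at every rate, so it also turns away doses that meet the plan's own definition. Exact one-sided 95% upper limits are 63% after 0/3, 39% after 0/6 and 58% after 1/6. All exceed one-third, so confidence limits do not single out six.

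Third, at least six patients are treated before any RP2D at 90 mg. The expansion itself is meant to confirm safety, and 10.5 provides for team review of toxicity logs and DSMC review. This is fair context, but no threshold is attached to those reviews.

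Stronger readings that a reader might infer are not supported:
- That the plan settles on three patients. This is only one side of the contradiction; 5.2.2 allows 3 to 6.
- That 0/3 fails the MTD definition. Taken literally, 0/3 is below one-third and meets it.
- That 45 mg becomes the RP2D on 0/3 if the higher doses fail. No section makes it the fallback.

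**Conclusion.** The point holds as an internal contradiction with a missing rule. The 9 implies six patients at 90 mg and a minimum total of 41; the 38 implies three. Sections 2.0, 5.2.2 and 8.1 do not decide, and nothing implies six at 60 mg. As written, an RP2D could therefore be declared on 0/3 at that dose. Against a requirement of at most 1 DLT in 6, this raises acceptance of a dose whose true DLT rate is one-third to one-half by 6.3 to 7.7 percentage points. These sizes rest on assumed true rates, independent patients and the usual expansion after 1 DLT in 3. The conflict between 9 and 38 rests on none of these; it is arithmetic on the plan's own figures, with the 32 counted as additional as in 2.0. It should be corrected because it concerns the decision rule for the primary objective.

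**What to change.** Reconcile the 9 with the 38, and state in 5.2.2 and 8.1 the minimum number of DLT-evaluable patients required at a dose before it is declared the RP2D, for 60 mg as well as 90 mg.

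- **If the six implied by the 9 is intended:** let the first three expansion patients who start on the combination complete the six, and open the remaining places once they clear the DLT window. Patients assigned to pembrolizumab alone in cycle 1 cannot count. Then 9 + 29 = 38, and the two figures agree. The sentence that ties the start of the expansion to a determined RP2D needs matching wording.
- **If three are intended:** restate the 9 as 6, and say openly that the RP2D may rest on 0/3.

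The second option costs only wording. The first costs a pause of about one DLT window, which is 21 days in 5.2.3 but 4 weeks in 2.0; those two must also be reconciled. Acceptance of tolerable doses falls by about 2 points at a true rate of 10%, 5 at 20% and 7 at 30%. If the dose is rejected on the three added patients, up to three expansion places must be replaced. The total still stays within 50, because 6 + 6 + 6 + 32 = 50 remains the ceiling.

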## 5.0 METHODOLOGY

### 5.1 Entry Criteria

#### 5.1.1 Diagnosis/Condition for Entry into the Trial

- a. In the dose escalation phase, the trial will be open for patients with stage IV or locally advanced unresectable gastrointestinal adenocarcinomas (gastric, GEJ, cholangiocarcinoma, hepatocellular, pancreas, small intestinal tumors) who have failed at least one prior therapy. Patients with colorectal cancer must have previously received oxaliplatin, irinotecan, and a fluoropyrimidine.
- b. In the dose expansion phase, Arm A will be open for 16 patients with pancreatic adenocarcinoma. Patients must have histologic diagnosis and either locally advanced unresectable or metastatic disease that has failed at least one standard regimen. Eight patients will participate in the paired biopsy studies. Patient selected for biopsy must have a primary or metastatic non-bone site that is amenable to safe biopsy. Bone only lesions are not suitable for biopsy. These patients will provide informed consent for the paired biopsy study.
- c. In dose expansion phase, Arm B will be open for 16 patients with colorectal adenocarcinoma. Patients must have histologic diagnosis and either locally advanced unresectable or metastatic disease and have previously received oxaliplatin, irinotecan, and a fluoropyrimidine. Eight patients will participate in the paired biopsy studies. Patient selected for biopsy must have a primary or metastatic non-bone site that is amenable to safe biopsy. Bone only lesions are not suitable for biopsy. These patients will provide informed consent for the paired biopsy study.

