9. Has a known additional malignancy that is progressing or requires active treatment. Exceptions include basal cell carcinoma of the skin or squamous cell carcinoma of the skin that has undergone potentially curative therapy or in situ cervical cancer.
  10. Has known active central nervous system (CNS) metastases and/or carcinomatous meningitis. Subjects with previously treated brain metastases may participate provided they are stable (without evidence of progression by imaging for at least four weeks prior to the first dose of trial treatment and any neurologic symptoms have returned to baseline), have no evidence of new or enlarging brain metastases, and are not using steroids for at least 7 days prior to trial treatment. This exception does not include carcinomatous meningitis which is excluded regardless of clinical stability.
  11. Has active autoimmune disease that has required systemic treatment in the past 2 years (i.e. with use of disease modifying agents, corticosteroids or immunosuppressive drugs). Replacement therapy (eg., thyroxine, insulin, or physiologic corticosteroid replacement therapy for adrenal or pituitary insufficiency, etc.) is not considered a form of systemic treatment.
  12. Has known history of, or any evidence of active, non-infectious pneumonitis.
  13. Has an active infection requiring systemic therapy.
  14. Has known substance abuse disorders that would interfere with cooperation with the requirements of the trial.
  15. Is pregnant or breastfeeding, or expecting to conceive or father children within the projected duration of the trial, starting with the screening visit through 120 days after the last dose of trial treatment.
  16. Has received prior therapy with an anti-PD-1, anti-PD-L1, anti-PD-L2, or HSP inhibitor.
  17. Has a known history of Human Immunodeficiency Virus (HIV) (HIV 1/2 antibodies).
  18. Has known active Hepatitis B (e.g., HBsAg reactive) or Hepatitis C (e.g., HCV RNA [qualitative] is detected).
  19. History of malabsorption or other condition that would interfere with absorption of study drugs.

20. History of or evidence of retinal pathology on ophthalmologic examination that is considered a risk factor for neurosensory retinal detachment, RVO (retinal vein occlusion), or neovascular macular degeneration. The risk factors for RVO are listed below. Patients should be excluded if they have the following current conditions:

- a. Uncontrolled glaucoma with intra-ocular pressures > 21mmHg

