#### **7.1.2.7 Tumor Tissue Collection and Correlative Studies Blood Sampling**

Pre- and post- treatment tumor biopsies will be obtained from 16 patients enrolled on the expansion phase. Patients will sign the optional biopsy consent prior to starting treatment and will be assigned to either start pembrolizumab or pembrolizumab/XL888 for the first cycle. Biopsies will be obtained within 4 weeks prior to the first dose of study therapy (biopsy #1) and then during the third week between Day 14 and Day 20. At least three core biopsies will be obtained at the time of the biopsy (unless limited for technical/safety reasons). The obtained tissues will be handled in the following way:

- 1) RNAlater for RNA stabilization and tissue storage
- 2) Formalin-fixed paraffin block with one cut H&E stained slide
- 3) Liquid nitrogen frozen tissue in cryo-preservation vials

All collected tissues are stabilized and stored in -80°C freezers (RNAlater stabilized, OCT embedded, short term storage) or the vapor phase of a liquid nitrogen freezer (long term storage) in single use aliquots. All FFPE tissue blocks are stored in a climate controlled storage room that is temperature (less than 27°C) and humidity controlled.

Tissue will be evaluated using IHC for CD3, CD4, CD8, CD163, PD-1, PD-2, PDL-1, MIF, TAM and stromal/ vascular markers. Tissue will also be dissociated and flow cytometry will be used to determine the characteristics of macrophages and lymphocytes. Genomic (transcriptome) profiling will be performed on tissue and lymphocytes.

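### The 20% response benchmark assumes minimal checkpoint-inhibitor activity in all colorectal patients, yet the plan does not ask for mismatch-repair (MSI) status, so PD-1-sensitive tumours in Arm B could not be recognised

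*Combined protocol and SAP*

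**What the plan says.** Section 8.1 of the combined protocol and SAP opens its response argument with "Given minimal activity of checkpoint inhibitors in colorectal and pancreatic cancer". It continues that "an overall response rate of the combination of PD-1 plus HSP90 inhibitor of 20% would be considered clinically significant". The error rate and power follow ("With an alpha of 0.1, and power of 80" per cent), and then the conclusion that "a total of 16 patients should be sufficient to make this determination". It gives no null response rate, no sidedness for alpha and no number of responders that would count as success.

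Section 5.1.1(c) says "Arm B will be open for 16 patients with colorectal adenocarcinoma". The disease must be unresectable or metastatic, and patients must "have previously received oxaliplatin, irinotecan, and a fluoropyrimidine". Section 5.1.3 excludes anyone who "Has received prior therapy with an anti-PD-1, anti-PD-L1, anti-PD-L2, or HSP inhibitor", so every Arm B patient is new to checkpoint inhibition.

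No readable text names mismatch repair or microsatellite instability. I looked in the eligibility criteria (5.1.2, 5.1.3), disease details (7.1.1.5), tissue assays (7.1.2.7), the laboratory table, the screening list (7.1.4.1), the analysis sets (8.4) and the baseline summaries (8.5). The tissue panel is listed as follows: "Tissue will be evaluated using IHC for CD3, CD4, CD8, CD163, PD-1, PD-2, PDL-1, MIF, TAM and stromal/ vascular markers".

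Under 8.1, some expansion patients start on pembrolizumab alone, but everyone receives the combination after three weeks. Section 7.1.4.4 puts the first on-treatment scan at days 15 to 21 of cycle 3.

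**The concern.** The trial's hypothesis (4.2) is that HSP90 inhibition strengthens the response to PD-1 blockade. Response has no comparator: the pembrolizumab-alone lead-in ends after day 21, and the first scan falls on days 57 to 63 (two 21-day cycles plus 15 to 21 days). Any inference from an Arm B response rate to a combination effect therefore depends on the minimal-activity premise holding for the patients actually enrolled.

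That premise is stated for colorectal cancer as a whole. If a few enrolled tumours are sensitive to PD-1 blockade alone, their responses enter the Arm B rate like any others. Nothing in the plan lets a reader find them afterwards. With 16 patients, one or two responses change the picture. What is at stake is how the preliminary activity result is read. The recommended phase 2 dose and the safety conclusions are not affected.

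**Working it through.** **Inputs from the documents:** n = 16 in Arm B, target rate 20%, alpha 0.1, power 80% (all 8.1).

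**Inputs assumed, not in the documents:** some colorectal tumours are MMR-deficient and respond to pembrolizumab alone. Central values are a response rate q = 40% in them and p0 = 2% in the rest. Ranges are shown below.

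**1. The plan's own figure.** With no null rate or cut-off, 16 cannot be reproduced uniquely. For a cut-off of two responders, P(X ≥ 2) = 1 − (1−p)^16 − 16p(1−p)^15.
- At p = 20%: 1 − 0.0281 − 0.1126 = 85.9%, which meets the 80% target.
- With alpha read as one-sided, this stays at or below 0.10 only for null rates up to 3.37%. At a 5% null it is 18.9%.
- Three of 16 has 64.8% power at 20%, and four of 16 has 40.2%.

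So two is the largest cut-off that keeps the stated power, and it needs a very low null rate. This cut-off is inferred. The plan does not state it.

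**2. No PD-1-sensitive patient.** At p0 = 2%: 1 − 0.7238 − 0.2363 = 4.0%.

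**3. One such patient among 16.** The other 15 give P(≥1) = 0.2614 and P(≥2) = 0.0353.
0.4 × 0.2614 + 0.6 × 0.0353 = 0.1258, or 12.6%.

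**4. Two such patients.** The other 14 give P(≥1) = 0.2464 and P(≥2) = 0.0310.
0.16 × 1 + 0.48 × 0.2464 + 0.36 × 0.0310 = 0.2894, or 28.9%.

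**5. Sensitivity, chance of two or more responses with no XL888 effect**

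| Sensitive patients | q = 30%, p0 = 2% | q = 40%, p0 = 2% | q = 50%, p0 = 2% | q = 40%, p0 = 1% | q = 40%, p0 = 3% |
|---|---|---|---|---|---|
| 0 | 4.0% | 4.0% | 4.0% | 1.1% | 8.2% |
| 1 | 10.3% | 12.6% | 14.8% | 6.2% | about 19% |
| 2 | 20.9% | 28.9% | 38.1% | 22.6% | 35.0% |

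**6. How likely at least one is.** 1 − (1−f)^16 gives 38.6%, 56.0%, 81.5% and 92.6% for assumed shares f of 3%, 5%, 10% and 15%.

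**7. A different cut-off.** Blended Arm B rates under assumed extremes, with p0 = 2%:
- 5% share, q = 30%: 0.05 × 0.30 + 0.95 × 0.02 = 3.4%.
- 15% share, q = 50%: 0.15 × 0.50 + 0.85 × 0.02 = 9.2%.

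For these two rates, P(≥2 of 16) is 10.1% and 44.0%. P(≥4 of 16), the count at which the observed rate first reaches 20%, is 0.2% and 5.3%. The size depends heavily on a cut-off that the plan leaves open.

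**The case against.** The strongest objection is that the documents nowhere say that MMR-deficient tumours respond to PD-1 blockade alone. A reader might infer that the premise in 8.1 is shown to be false for part of Arm B. It is not. The share, the response rate in deficient tumours and the background rate are all assumed. The premise and the eligibility criterion also describe the same disease, so a whole-disease statement of minimal activity may already average over a responsive minority. Adding a deficient fraction on top could then count it twice. All of this stands. What remains without any outside fact is structural: an unqualified premise, no stated null rate, no response comparator and no specified data item with which to check the premise.

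A reader might also infer a false-positive rate of 10% to 44%. The plan has no decision rule to which such a rate could attach. Section 8.3 rules out formal testing, and two of 16 is 12.5%, below the 20% benchmark.

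Nor do the documents show that status goes unrecorded. Disease details are collected in general terms (7.1.1.5), transcriptome profiling is planned on tissue (7.1.2.7), the case report form is not included, and part of the flow chart is illegible. Only the absence of a named item in readable text is established.

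Finally, response is secondary and described as preliminary (3.2), and 8.1 gives confirming safety and tolerability as the aim of the expansion. That lowers the severity. It does not remove the point, because 8.1 also says the 16 patients suffice to judge response.

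**Conclusion.** The point holds as a low-severity gap in interpretability. Section 8.1 applies one premise to all colorectal patients without giving a rate, Arm B has no MMR/MSI criterion, and no readable section specifies recording the status. If one or two PD-1-sensitive tumours drove the Arm B rate, the planned data would not show it.

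Under the central assumptions, one such patient moves the chance of two or more responses by 8.6 percentage points (12.6 − 4.0) and two move it by 24.9 (28.9 − 4.0). Both figures depend on the assumed response rates and the inferred cut-off, and they shrink greatly if four responders are required. Recording status would not supply a comparator. Separating single-agent from combination effects remains beyond this single-arm design.

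**What to change.** Add one baseline case report form field for MMR/MSI status in Arm B, taken from the existing pathology report and coded deficient, not deficient or unknown. Add one sentence to 8.1 and 8.3: the Arm B response rate is reported on all 16 patients, responses are also listed by status, and the 20% benchmark is read alongside the rate that excludes known-deficient patients.

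The cost is one field and one sentence. The rate excluding known-deficient patients rests on slightly fewer than 16, and some statuses will be unknown.

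Two stronger remedies are not warranted. New tissue testing should not be required: the tissue footnote in the flow chart refers only to paired biopsies from 16 expansion patients, so archival tissue for every patient is not established. The benchmark should not be confined to patients of known status either: with 13 patients left, the chance of two or more responses at a true 20% rate is 76.6%, below the planned 80%.

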#### **4.2.1 Rationale for Endpoints**

- 4.2.1.1 Efficacy Endpoints:** This is a phase I trial. The primary endpoint is still toxicity. The plan is to evaluate the response rate, response duration, and progression free

survival of the patients on the trial. These endpoints will provide preliminary data in two patient subsets: patients with pancreatobiliary and other GI malignancies.

- 4.2.1.2 **Biomarker Research:** We intend in all patients to evaluate the effects of the combination on T-cell population in peripheral blood. In addition, we plan to evaluate the effects of the combination versus pembrolizumab alone in paired biopsy samples in 16 patients. These samples will be analyzed for tumor infiltrating lymphocytes, stromal/tumor markers and expression immune inhibitory molecules (PD-L1, PD-L2, PD1, etc). We anticipate to see a difference between the group treated with the combination versus the group treated with pembrolizumab alone.

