### **5.3.3 Timing of Dose Administration**

Trial treatment should be administered on Day 1 of each cycle after all procedures/assessments have been completed as detailed on the Trial Flow Chart (Section 6.0). Trial treatment may be administered up to 3 days before or after the scheduled Day 1 of each cycle due to administrative reasons.

All trial treatments will be administered on an outpatient basis.

**Pembrolizumab** 200 mg will be administered as a 30 minute IV infusion every 3 weeks. Given the variability of infusion pumps, a window of -5 minutes and +10 minutes is permitted (i.e., infusion time is 30 minutes: -5 min/+10 min).

The Pharmacy Manual contains specific instructions for the preparation of the pembrolizumab infusion fluid and administration of infusion solution.

**XL888** will be administered twice weekly (days 1 and 4) orally starting on day 1 of every 3-week cycle.

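### The planned biopsy contrast of the combination with pembrolizumab alone rests on PI-chosen cycle 1 treatment, so a difference may reflect selection rather than XL888

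*Combined protocol and SAP*

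**What the plan says.** Three parts of the combined protocol and SAP bear on this point.

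- **The contrast.** Section 4.2.1.2 states: "we plan to evaluate the effects of the combination versus pembrolizumab alone in paired biopsy samples in 16 patients". It adds: "We anticipate to see a difference between the group treated with the combination versus the group treated with pembrolizumab alone". No marker, effect size or SD is given.
- **The assignment.** Section 8.1 states: "Patients in the expansion phase will be assigned to treatment arms by PI (MK-3475 or MK-3475 plus XL-888"). Section 7.1.2.7 says biopsy patients are assigned to one treatment or the other for the first cycle only. By 8.1, everyone receives the combination after the first 3 weeks. Section 8.1 words the assignment as covering all expansion patients; sections 2.0 and 7.1.2.7 apply it to the 16 biopsy patients. No section describes a randomisation procedure, concealment, stratification by tumour type or an adjusted analysis.
- **The analysis.** Section 8.1 also states: "There is no planned comparison between the two arms". Section 8.3 describes the analyses as hypothesis generating, without formal testing, but allows exploratory tests.

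The 16 biopsy patients are divided in two ways. By tumour type (pancreatic, colorectal), section 2.0 says: "Paired biopsy performed on 8 patients in each group". By treatment, it says: "Patients undergoing paired biopsies will be assigned into two treatment cohorts (8 in each) and treated according to the schema below". The readable text does not connect the two divisions.

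**The concern.** The pembrolizumab-alone cohort is the only part of the trial in which biopsied patients have XL888 withheld while others receive it. The hypothesis in 3.3 is that the HSP90 inhibitor alters the micro-environment. Change from baseline within the combination cohort cannot separate that effect from pembrolizumab's own, so the between-cohort contrast is the only concurrent evidence on it.

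The trial is open-label (5.3.4), so a PI who chooses the cohort knows each patient's fitness, disease burden and tumour type. Any of these could be related to how the tumour immune profile changes over three weeks. A difference between cohorts could then come from who was placed where. Section 8.1 expects the biopsy results to help further develop the combination, so a misleading signal would have consequences even though the analysis is exploratory. Sections 4.2.1.2 and 8.1 also leave it unclear whether the contrast will be made at all.

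**Working it through.** The plan gives no sample-size calculation for the biopsy contrast, so there is no figure to reproduce. The alpha of 0.1 and 80% power in 8.1 belong to the response rate. The calculations below only show scale.

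**Inputs from the documents.** 16 biopsy patients: 8 pancreatic and 8 colorectal, and also 8 per treatment cohort (2.0, 5.1.1).

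**Assumptions.** The documents give no marker data. Let d be the difference between tumour types in mean on-treatment change, in units of the SD within tumour type, and take d = 0.5, 1.0 and 1.5. Because the biopsies are paired, d must refer to change; stable differences in level cancel. XL888 is taken to have no effect.

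**Step 1: spurious difference.** If k of the 8 patients in one cohort have one tumour type and the other cohort is the mirror image, the tumour-type shares differ by k/8 − (8 − k)/8. The spurious cohort difference is therefore d × (2k − 8)/8.

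| Split | d = 0.5 | d = 1.0 | d = 1.5 |
|---|---|---|---|
| 4:4 v 4:4 | 0 | 0 | 0 |
| 6:2 v 2:6 | 0.25 SD | 0.50 SD | 0.75 SD |
| 8:0 v 0:8 | 0.50 SD | 1.00 SD | 1.50 SD |

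**Step 2: what 8 versus 8 can detect.** For a two-sample t-test with 14 degrees of freedom, the noncentrality is d × √(8/2) = 2d. Power of 80% is reached at d = 1.51 (two-sided 0.05) or 1.31 (two-sided 0.10). Against 1.51 SD, the 6:2 split gives 0.25/1.51 = 17% to 0.75/1.51 = 50% of the detectable difference. The complete split gives 0.5/1.51 = 33% to 1.5/1.51 = 99%.

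**Step 3: how often an exploratory test would mislead.** Chance of p < 0.05 in an unadjusted two-sided t-test with no XL888 effect (200,000 simulated trials per cell):

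| Split | d = 0.5 | d = 1.0 | d = 1.5 |
|---|---|---|---|
| 4:4 v 4:4 | 4.4% | 2.8% | 1.5% |
| 6:2 v 2:6 | 7.0% | 11.3% | 16.5% |
| 8:0 v 0:8 | 15.4% | 46.3% | 79.7% |

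The 4:4 row falls below 5% because an unadjusted test counts the tumour-type difference as noise. A balanced design should therefore be analysed with adjustment for tumour type.

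**Step 4: why stratify as well as randomise.** If 8 of the 16 are drawn at random without stratification, P(4:4) = 70²/12,870 = 38.1%. P(6:2 or more extreme) = 2 × (784 + 64 + 1)/12,870 = 13.2%. Stratification fixes 4:4 and sets the tumour-type contribution to zero. Random assignment within tumour type also removes PI selection on fitness or disease burden, which balance on tumour type alone would not.

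**Step 5: biopsy timing.** Section 7.1.2.7 places the second biopsy as follows: "then during the third week between Day 14 and Day 20". The section headed for days 14-21 of cycle 1 (numbered 7.1.4.3, a number used twice) allows one day more. Section 5.3.3 adds: "Trial treatment may be administered up to 3 days before or after the scheduled Day 1 of each cycle due to administrative reasons". With 3-week cycles, cycle 2 Day 1 is Day 22, so the earliest dose is Day 22 − 3 = Day 19. On calendar days alone, the windows overlap.

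**The case against.** The strongest reply is that little depends on this contrast. Section 8.3 makes the biomarker work hypothesis generating, 8.1 gives the expansion aim as safety and tolerability, and the recommended phase 2 dose is untouched. Non-randomised correlative cohorts are a defensible choice in a phase I expansion. That lowers the priority. It does not reconcile 8.1 with 4.2.1.2, where a between-group difference is expected. It could also be said that the two arms in 8.1 are the tumour-type Arms A and B of 2.0. The nearer reading is the treatment arms named just before. On either reading, no analysis of the 4.2.1.2 contrast is specified.

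Four stronger readings are tempting, and the documents do not support them.

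- **That treatment cohort and tumour type are confounded, or that nothing prevents it.** Section 2.0 refers to a schema that could not be read here and may fix the split. Tumour type is also known for every patient, so an imbalance would be visible and, unless complete, results could be shown by tumour type. A fixed split would still not remove the PI's choice within tumour type.
- **That the bias is 1 SD, or any particular size.** The documents give no marker data; every figure above depends on the assumed d, and 8:0 is a worst case.
- **That pembrolizumab-alone biopsies will be taken after a first XL888 dose.** Section 5.3.3 has the flow-chart procedures completed before Day 1 treatment. The flow chart marks tissue collection at screening and cycle 1 only, and the repeat biopsy is listed as a cycle 1 procedure. What remains is a wording mismatch between the windows.
- **That PI choice makes the contrast worthless and randomisation fully restores it.** PI choice weakens it. Randomisation removes the selection but leaves 8 versus 8 across many markers, with 4 patients per tumour-by-treatment cell.

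**Conclusion.** The point holds as a moderate, inexpensive improvement to an exploratory analysis. The plan states and expects a between-cohort biopsy difference, leaves the cohort to the PI in an open-label trial, specifies no adjustment, and says elsewhere that no comparison is planned. These statements need to be reconciled, and the assignment method should match whichever aim is kept.

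The possible size is illustrative. If tumour types differ by 0.5 to 1.5 SD in on-treatment change, the spurious difference is 0.25 to 0.75 SD for a 6:2 split and 0.5 to 1.5 SD for a complete split, against about 1.5 SD detectable. This rests on the assumed range for d, no XL888 effect, mirror-image cohorts, and the schema not already fixing the split. Selection on fitness or disease burden would come in addition and cannot be sized from the documents. The dose-finding conclusion is unaffected.

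**What to change.** Preferred change:

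1. In 8.1, 2.0 and 7.1.2.7, replace PI assignment of biopsy-consenting patients with 1:1 randomisation stratified by tumour type (4:4 in pancreatic, 4:4 in colorectal), with the list held outside the clinical team. State that this applies to the biopsy patients only.
2. In 8.3, add that the between-cohort difference in on-treatment biopsy values, adjusted for the baseline biopsy and tumour type, will be reported with confidence intervals and labelled exploratory.
3. In 8.1, restrict the statement that no comparison is planned to clinical endpoints.

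This costs a list, a few sentences and the PI's discretion over cycle 1, with no extra patients, biopsies or visits. The contrast stays imprecise.

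Alternative: keep PI assignment, delete the expected between-group difference from 4.2.1.2, and report within-cohort changes only. This costs the ability to attribute a tumour change to XL888 rather than pembrolizumab.

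Under either option, as a minor point, reconcile the two biopsy windows (Day 14 to 20 and days 14 to 21) with each other and with the 3-day dosing window in 5.3.3.
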